#### b. Previous exposure of human beings with the test product(s) and/or products with a similar biological mechanism

There is tremendous experience with TIS as chronic treatment in CF-patients. In general practice it is well tolerated. Only few studies have been performed in non-CF bronchiectasis patients (see section 6.2 and 6.3). Although not registered, numerous patients are already treated with TIS (TOBI® and Bramitob®). These patients are tolerating TIS well and nebulizing this drug seems very effective (personal experiences of Dutch pulmonologists).

#### c. Can the primary or secondary mechanism be induced in animals and/or in ex-vivo human cell material?

Not applicable.

d. Selectivity of the mechanism to target tissue in animals and/or human beings

Not applicable.

e. Analysis of potential effect

see section 6.1, 6.2 and 6.3.

f. Pharmacokinetic considerations

see section 6.1 and 6.2.

g. Study population

non-CF bronchiectasis.

h. Interaction with other products

Combination with furosemide, ureum or mannitol should be avoided because of potential nephro- and/or ototoxicity. Especially, nephrotoxicity may occur in combination with IV prescribed aminoglycosides, amphotericin B, cephalosporins, polymyxins, ciclosporin, tacrolimus and platinum containing drugs. A combination with botulinetoxine or anticholinesterases (e.g., neostigmine, pyridostigmine) may induce a prolonged neuromuscular blockade.

i. Predictability of effect

Effect can possibly be measured by biomarkers (inflammation), lung function and bacterial load in sputum.

j. Can effects be managed?

Not applicable.

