Efficacy parameters will include assessment of pulmonary exacerbations, spirometry, LTRI-VAS, QOL-B and Leicester cough questionnaires. Microbiological response measurements will include semi-quantitative density of pathogens in sputum, including the tobramycin minimum inhibitory concentration (MIC) for isolated pathogens. Safety parameters will include assessment of AEs, serial spirometry findings, clinical laboratory test results, vital signs measurements, physical examination. Study drug is dispensed on the regular visits. The first patients will be enrolled in the summer of 2016, with a treatment period of 12 months, we expect to terminate the study 31-01-2020.

In subjects who experience a pulmonary exacerbation, every effort should be made to continue their allocated inhaled study drug, unless the study drug is not tolerated, or the pulmonary exacerbation is believed to be related to study drug. All subjects who receive any study drug need to complete the visit 7 assessments. Subjects who are prematurely withdrawn from study drug will be encouraged to

remain in the study and attend subsequent study visits; at a minimum, they should complete the visit 7 assessments as an early termination visit.

An independent expert will be established to conduct periodic reviews of subject safety for this protocol. The independent expert will also perform a blinded analysis of the pulmonary exacerbation data to check whether the assumptions for sample size estimation are valid, and if they are not, the sample size may be increased.

This study will be conducted in the Noordwest Ziekenhuisgroep, Canisius ZH Nijmegen, Spaarne Gasthuis Hoofddorp, Zuyderland MC Heerlen, VU Medical Center Amsterdam and UMC Utrecht.

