### 5.2 Use of co-intervention

All co-medications are allowed, except for any oral (except for macrolides), IV or inhaled antibiotics within 1 month prior to the start of the study and any IV or IM corticosteroids or change in oral corticosteroids (> 10 mg) within 1 month prior to the start of the study. Immunosuppressive agents such as azathioprine, chemotherapeutic agents, and TNF $\alpha$  inhibitors are prohibited. Also, any change/start treatment regimens of macrolides, hypertonic saline, inhaled mannitol or other mucolytics, within 1 month prior to the start of the study are prohibited. Also, the use of loopdiuretics, mannitol or urea are prohibited.

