### 5.3 Escape medication

In consultation with the own GP or respiratory physician the patient may use extra bronchodilators for relief of dyspnoea. In subjects who experience a pulmonary exacerbation, every effort should be made to continue their allocated inhaled study drug, unless the study drug is not tolerated, or the pulmonary exacerbation is believed to be related to study drug. All subjects who receive any study drug need to complete the visit 7 assessments. Subjects who are prematurely withdrawn from study drug will be encouraged to remain in the study and attend subsequent study visits; at a minimum, they should complete the visit 7 assessments as an early termination visit.

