## **6.6 Dosages, dosage modifications and method of administration**

See 6.5

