## **7.3 Study procedures**

Patients with bronchiectasis and who fulfil the inclusion and exclusion criteria will be asked to participate in the study. After a run-in period of 4 weeks' patients will be randomized to receive one of the two possible treatment regimens: TIS OD 300 mg daily or placebo. Administration will be continuous for the full 12 months. According to the parallel group design patients will be treated for 52 weeks. After completing the intervention period patients will have a follow-up (wash out period) of 4 weeks. This wash-out period was considered to be one month, in which time the antimicrobial effect of the antibiotic supposedly disappears, as suggested in earlier studies.

Subjects will be evaluated at run-in = visit 0 (week -4), visit 1 (day 1- start of the study), visit 2 (week 13), visit 3 (week 26), visit 4 (week 39), visit 5 (week 52: end of treatment) and visit 6 (run-out; week 56: end of the study). One week after start of treatment a phone call will be scheduled. Clinical, laboratory, and bacteriology evaluations will be determined according to the schedule (Figure 1: study schedule). Subjects who terminate treatment should be followed for the same period as those who complete the study, according to the study schedule.

During the study any changes in medical condition and compliance with medication will be filed in the diary card.

At visit 1, after randomisation, a tolerance test with either TIS or placebo (blinded according to randomisation) will be performed. Before nebulizing TIS patients are treated with salbutamol 200mcg using an AeroChamber. During tidal breathing patients inhale 300mg TIS or placebo (at room temperature) by using the Innospire Deluxe nebulizer with mouthpiece during approximately 5 minutes. If patients develop a moderate-severe bronchial obstruction, patients are excluded from the study. The severity of bronchial obstruction and coughing is assessed by a specialized nurse, the respiratory physician or the own GP. An exacerbation is defined as the presence of three or more of the following symptoms or signs for at least 24 hours: increased cough, increased sputum volume, increased sputum purulence, haemoptysis, increased dyspnoea, increased wheezing, fever (>38.5°C)

or malaise, and the treating physician agreed that antibiotic and/or prednisolone therapy was required.

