### **7.6 Follow-up of subjects withdrawn from treatment**

Follow-up of patients withdrawn from treatment have an out-patient visit following the study schedule. These patients will be evaluated the same as the patients who complete the study. Subjects will be evaluated at run-in = visit 0 (week -4), visit 1 (day 1- start of the study), visit 2 (week 13), visit 3 (week 26), visit 4 (week 39), visit 5 (week 52: end of treatment) and visit 6 (run-out; week 56: end of the study). One week after start of treatment a phone call will be scheduled. During an exacerbation the patient will contact his/her own GP or specialist.

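### The instruction to continue study drug through an exacerbation has no exception or renal check for the IV antimicrobials that section 12.1h flags for nephrotoxicity

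*Combined protocol and SAP*

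**What the plan says.** Section 12.1, item h, grades its warnings. Furosemide, urea and mannitol are to be avoided. For a second group the wording is weaker: "nephrotoxicity may occur in combination with IV prescribed aminoglycosides, amphotericin B, cephalosporins, polymyxins, ciclosporin, tacrolimus and platinum containing drugs".

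Section 5.2 makes loop diuretics, mannitol and urea prohibited. It also bars immunosuppressive and chemotherapeutic agents, which arguably deals with ciclosporin, tacrolimus and platinum drugs. On antimicrobials it says: "All co-medications are allowed, except for any oral (except for macrolides), IV or inhaled antibiotics within 1 month prior to the start of the study". That is an entry restriction, and nothing in it applies once treatment has begun.

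For a patient with an exacerbation, section 5.3 says that "every effort should be made to continue their allocated inhaled study drug, unless the study drug is not tolerated". Section 3 carries the same instruction, and both sections give the same two exceptions: "unless the study drug is not tolerated, or the pulmonary exacerbation is believed to be related to study drug". Section 6.6, headed "Dosages, dosage modifications and method of administration", only points to section 6.5, which contains no hold, restart or renal rule.

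Stopping study drug is allowed for. Section 5.3 states: "Subjects who are prematurely withdrawn from study drug will be encouraged to remain in the study and attend subsequent study visits". Section 7.6 adds: "Follow-up of patients withdrawn from treatment have an out-patient visit following the study schedule". Both describe patients taken off treatment, not a pause followed by a restart.

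**The concern.** An exacerbation is the trial's endpoint event, and it is also when an IV aminoglycoside, cephalosporin or polymyxin is most likely to be given. In that event the protocol's default is to continue inhaled tobramycin, itself an aminoglycoside (section 5.1). The prescriber may be a GP or a chest physician (sections 7.1.3 and 7.3) who is blind to the arm. Section 7.3 bases the choice of antibiotic on microbiology and tolerance, without mention of an interaction. Section 12.1, item j, which asks whether effects can be managed, is answered as not applicable.

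At stake is a patient kept on tobramycin during an IV course that the protocol itself flags, with no study renal test requested in that course. Systemically absorbed tobramycin is cleared mainly by glomerular filtration (section 6.2.4), and patients may enter with an eGFR as low as 30 ml/min (section 4.3).

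**Working it through.** **1. Is there a rule anywhere?** The safeguards, set against the event of a listed IV drug being prescribed:

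- Section 7.1.3: the investigator is informed of exacerbation treatment. No renal test or hold follows.
- Section 7.3: patients have 24-hour contact details. No action is tied to a co-prescription.
- Section 7.3 visit lists: creatinine and eGFR at weeks -4, 13, 26, 39, 52 and 56, by calendar. No laboratory test is listed at visit 1.
- Section 7.4: withdrawal from the study for urgent medical reasons. This is not a pause.
- Sections 8.2.2 and 8.2.3: a hospital admission is reported as an SAE; the coordinating physician can break the code. Neither prompts a renal test.
- Section 8.5: expert review every three to six months, too slow to act within a course.
- Appendix 4: stopping the inhaled drug is the stated remedy once an unwanted effect appears.

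None is triggered by the prescription, and no restart rule is written.

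**2. Would a scheduled test fall inside the course?** Assume a course of 10 to 14 days starting at random in a 13-week (91-day) interval. The chance is 10/91 = 11.0% to 14/91 = 15.4%.

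**3. How many courses?** The documents do not give this. At the planning rate (sections 4.4 and 9.1) the TIS arm has 29 x 2.1 x 0.5 = 30.45 exacerbations in a year, or 30.45 x 0.7 = 21.3 if the 30% who drop out gave no time on drug. These are not all antibiotic courses, because the definition requires only that "the treating physician agreed that antibiotic and/or prednisolone therapy was required". With an assumed share on a listed IV drug:

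- 5%: 21.3 x 0.05 = 1.1 to 30.45 x 0.05 = 1.5 courses.
- 20%: 21.3 x 0.20 = 4.3 to 30.45 x 0.20 = 6.1 courses.

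**4. What do the renal data show?** Section 6.4 reports nine patients (3%) in each group with a creatinine rise of at least 50%. Taking the 258 patients as the TIS group, 9/258 = 3.5%, consistent with the printed 3%; the 95% Clopper-Pearson interval is 1.6% to 6.5%. If the placebo group was of equal size (assumed), the difference is 0 with a half-width of 1.96 x sqrt(2 x 0.0349 x 0.9651/258) = 3.2 percentage points. Creatinine fell at the next visit in all nine TIS patients. These were CF patients on 28-day on/off dosing, and overlap with IV courses is not reported.

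**5. What would a hold cost?**

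- Arm level: a 14-day hold (assumed) in 5% to 20% of exacerbations loses 30.45 x 0.05 x 14 = 21.3 to 30.45 x 0.20 x 14 = 85.3 days, out of 29 x 364 = 10,556. That is 0.2% to 0.8%.
- Patient level, as a stress case from the CF figures in section 6.3: 9.6 parenteral days on average with 40% treated gives 9.6/0.40 = 24 days per treated patient in 24 weeks (168 days). Continued for a year, 24 x 364/168 = 52 days, or 7.4 weeks. Held throughout, this leaves 52 - 7.4 = 44.6 weeks, against a nine-month minimum of 52 x 9/12 = 39 weeks (section 9.3.3).
- Extra tests, both arms: (29 x 2.1 + 30.45) = 91.35 exacerbations; x 0.05 = 4.6 and x 0.20 = 18.3. At the CF shares of 40% and 53%, 29 x 0.40 + 29 x 0.53 = 27 patients in six months would need at least one.

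**The case against.** The strongest reply is that the protocol grades its warnings on purpose. Drugs to be avoided became prohibitions. Drugs that may cause nephrotoxicity were left to the treating physician, who can judge tolerance, stop study drug, withdraw the patient or ask for the code to be broken. Asking for every effort does not forbid a pause. Patients with an eGFR below 30 ml/min never enter. Exposure is low: mean serum tobramycin one hour after a dose was 0.95 mcg/mL, and 1.05 mcg/mL after 20 weeks (section 6.2.3), and this trial doses once daily against the twice-daily CF regimen described in section 1. A hospital giving IV antibiotics may well test creatinine anyway, and the SPC, which is not in the documents, may already cover the combination.

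Most of this stands, and it limits the weight of the point. It does not remove it. Discretion to stop works chiefly after a problem appears, and the written default still leans towards continuing. Low serum levels bear on the size of an interaction but do not exclude one.

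Three stronger readings are tempting and are not supported. A reader might infer that the protocol breaks its own ban; item h is a caution for these drugs, so no ban exists. A reader might infer that renal function goes unmonitored; it is tested about every 13 weeks. A reader might infer that excess renal harm is shown; the only comparative figures are equal in the two arms, in another population.

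The scope of item h is also unclear: the reference to IV use may govern the aminoglycosides alone or the whole list. The counts above take the IV-only reading; the wider one would add courses.

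**Conclusion.** The point holds as a minor safety gap. A stated default runs against the protocol's own caution in the event where the two are most likely to meet, and no section supplies a triggered renal check or an interrupt-and-resume rule.

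Its size cannot be derived from the documents. The range of 1 to 6 TIS-arm courses rests on assumed shares of 5% and 20%. The CF figure of 40% in six months covers any parenteral anti-pseudomonas antibiotic in a different disease, so it is a stress case and not an estimate. The renal data neither show nor exclude a risk from the combination. The case for change is that the correction is cheap, not that harm is likely to be large.

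**What to change.** In sections 3 and 5.3 add a third exception, identical in both blinded arms and cross-referenced from sections 5.2 and 6.6. When an antimicrobial named in section 12.1h is prescribed during treatment:

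- the investigator is informed, through the route already in section 7.1.3;
- creatinine and eGFR are checked during the course;
- study drug may be interrupted and resumed afterwards.

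Make interruption the default for an IV aminoglycoside, because study drug may be one. Leave the other classes to the clinician and the SPC. State in item h whether the IV qualifier covers the whole list. Because the rule applies to both arms, no unblinding is needed.

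The cost is a few lines of text, about 5 to 18 routine blood tests across both arms at the assumed shares (more at CF rates of use), and 0.2% to 0.8% of TIS dosing days. A patient treated for the full year should stay above the per-protocol minimum even in the stress case. A patient who stops near nine months has little room, so section 9.3.3 should say whether held days count towards the nine months.

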## **12.2 Synthesis**

Because of the previous experience with TIS in CF patients, but also in non-CF patients there is low risk of toxicity. First dose of study drug administered under supervision of study staff may give information of the tolerance. A number of safety measurements are included: phone call after one week, other outpatient visits, serial laboratory testing, dairy card, and safety checks by the independent expert.

## Appendix 1. Lower Respiratory Tract Infection Visual Analogue Scale (LRTI-VAS) -Dutch edition-

# KLACHTEN SCHAAL

DAG:

Randomisatie nr.

--	--	--

Naam:

Zet a.u.b. een kruisje op de volgende lijnen:

### 1. KORTADEMIGHEID

Ik ben  
helemaal  
niet  
kortademig

Ik heb de ergst  
denkbare  
kortademigheid

### 2. VERMOEIDHEID

Ik ben  
helemaal  
niet moe

Ik heb de ergst  
denkbare  
moeheid

### 3. HOEST

Ik hoest  
helemaal  
niet

Ik heb de ergst  
denkbare  
hoest

### 4. WAT VOOR SPUTUM GEEFT U OP?

Wit sputum

Donker groen  
sputum

### 5. PIJN

Geen pijn

Ik heb de ergst denkbare pijn

**Appendix 2. Leicester Cough Questionnaire -Dutch edition-**

Naam:
Geboortedatum
Bezoeknummer:
Datum:

**HOEST VRAGENLIJST**

Deze vragenlijst is ontworpen om de gevolgen van het hoesten op diverse aspecten van uw leven te meten. Lees iedere vraag aandachtig en OMCIRKEL het antwoord dat de **afgelopen twee weken** het meest op u van toepassing is (slechts één antwoord per vraag). Beantwoord a.u.b. alle vragen, en zo eerlijk mogelijk.

In de afgelopen twee weken...	altijd	meesta l	heel vaak	regelm atig	af en toe	zelden	nooit
1. had u door het hoesten last van pijn op de borstkas of in de maag?	1	2	3	4	5	6	7
2. had u door het hoesten last van slijm ophoesten?	1	2	3	4	5	6	7
3. bent u door het hoesten vermoeid geraakt?	1	2	3	4	5	6	7
In de afgelopen twee weken...	nooit	zelden	af en toe	regelm atig	heel vaak	meesta l	altijd
4. had u het idee het hoesten onder controle te hebben?	1	2	3	4	5	6	7
In de afgelopen twee weken...	altijd	meesta l	heel vaak	regelm atig	af en toe	zelden	nooit
5. hoe vaak schaamde u zich voor het hoesten?	1	2	3	4	5	6	7
6. werd u ongerust door het hoesten?	1	2	3	4	5	6	7
7. verstoorde het hoesten uw werk of andere dagelijkse bezigheden?	1	2	3	4	5	6	7
8. bemerkte u dat het hoesten het plezier in het leven vergalde?	1	2	3	4	5	6	7
9. moest u hoesten van verflucht of andere prikkelende luchtjes?	1	2	3	4	5	6	7

10.	hoe vaak werd uw nachtrust verstoord door het hoesten?	1	2	3	4	5	6	7
11.	hoe vaak hoestte u op een dag?	1	2	3	4	5	6	7
12.	voelde u zich gefrustreerd door het hoesten	1	2	3	4	5	6	7
13.	was u het hoesten zat?	1	2	3	4	5	6	7
	In de afgelopen twee weken...	altijd	meestal	heel vaak	regelmatig	af en toe	zelden	nooit
14.	was u hees door het hoesten?	1	2	3	4	5	6	7
	In de afgelopen twee weken...	nooit	zelden	af en toe	regelmatig	heel vaak	meestal	altijd
15.	zat u vol energie?	1	2	3	4	5	6	7
	In de afgelopen twee weken...	altijd	meestal	heel vaak	regelmatig	af en toe	zelden	nooit
16.	was u bezorgd dat uw hoest door een ernstige ziekte veroorzaakt werd?	1	2	3	4	5	6	7
17.	was u bezorgd dat anderen dachten dat u wat ernstigs mankeerde, door uw hoesten?	1	2	3	4	5	6	7
18.	verstoorde uw hoest uw praten of een telefoongesprek?	1	2	3	4	5	6	7
19.	meende u dat het hoesten vervelend is voor uw partner, familie of vrienden?	1	2	3	4	5	6	7

Gebaseerd op de **Leicester Cough Questionnaire** © Birring

### Appendix 3. Quality of Life Questionnaire Bronchiectasis (QOL-B) -Dutch edition-

# QOL-B

## VRAGENLIJST KWALITEIT VAN LEVEN – BRONCHIËCTASIE

Het begrijpen van de impact van uw ziekte en behandelingen op uw dagelijks leven kan uw arts helpen uw gezondheid te controleren en uw behandelingen aan te passen. Om die reden hebben we een vragenlijst opgesteld om de kwaliteit van leven te meten, speciaal voor mensen met bronchiëctasie. Hartelijk dank dat u deze vragenlijst wilt invullen.

**Aanwijzingen:** De volgende vragen gaan over uw huidige gezondheidstoestand zoals u deze ervaart. Met deze informatie krijgen wij beter inzicht in hoe u zich in het dagelijks leven voelt.

Beantwoord alstublieft alle vragen. Er zijn **geen** goede of foute antwoorden! Als u niet zeker weet wat u moet antwoorden, kies dan het antwoord dat uw situatie het beste weergeeft.

#### Demografische gegevens

*Vul de gegevens in of vink het vakje aan bij uw antwoord.*

A. Wat is uw geboortedatum?

Datum 

--	--	--	--	--	--	--	--	--	--

  
Dag    Maand    Jaar

B. Wat is uw geslacht?

Man     Vrouw

C. Bent u de afgelopen week op vakantie geweest, of hebt u niet gestudeerd of niet gewerkt om redenen die **NIET** met uw gezondheid te maken hadden?

Ja     Nee

D. Wat uw huidige burgerlijke staat?

- Alleenstaand/nooit getrouwd  
 Getrouwd  
 Weduwe/weduwenaar  
 Gescheiden  
 Uit elkaar  
 Hertrouwd  
 Samenwonend

E. Welke van de volgende opties beschrijft het beste uw etnische achtergrond?

- Nederlands  
 Turks  
 Marokkaans  
 Surinaams  
 Antilliaans  
 Aziatisch  
 Anders (graag toelichten) \_\_\_\_\_  
 Deze vraag beantwoord ik liever niet.

F. Wat is uw hoogst genoten opleiding?

- Enkele jaren (of minder) voortgezet onderwijs  
 Diploma voortgezet onderwijs  
 MBO  
 Enkele jaren HBO  
 Diploma HBO  
 Diploma WO

G. Welke van de volgende opties beschrijft het beste uw huidige opleidings- of werksituatie?

- Ik volg buitenshuis een cursus/opleiding  
 Ik volg thuis een cursus/opleiding  
 Ik ben werkzoekend  
 Ik werk voltijds of deeltijds (buitenshuis, of vanuit huis)  
 Ik ben huisman/huisvrouw  
 Ik volg geen opleiding en heb geen werk vanwege mijn gezondheid  
 Ik werk niet om een andere reden/ik ben gepensioneerd

**Ga verder naar de volgende bladzijde**

Vragenlijst Kwaliteit van Leven – Bronchiëctasie

**Deel I. Kwaliteit van leven**

*Vink het vakje aan dat uw antwoord aangeeft.*

In welke mate had u gedurende de afgelopen week moeite met:	Veel moeite	Matige moeite	Beetje moeite	Geen moeite
1. Verrichten van inspannende activiteiten zoals tuinieren of fietsen .....				
2. Net zo snel kunnen lopen als anderen (familie, vrienden, enz.) .....				
3. Zware dingen dragen zoals boeken of boodschappentassen .....				
4. Eén trap oplopen .....				
 Geef aan hoe vaak u zich gedurende de afgelopen week zo voelde:				
	Altijd	Vaak	Soms	Nooit
5. U voelde zich goed .....				
6. U voelde zich moe .....				
7. U was gespannen/u maakte zich zorgen .....				
8. U voelde zich energiek .....				
9. U voelde zich uitgeput .....				
10. U voelde zich verdrietig .....				
11. U voelde zich depressief .....				

**Wordt u op dit moment behandeld (zoals met orale of te inhaleren geneesmiddelen, een PEP- of Flutter®-apparaat, borstfysiotherapie of Vest) voor uw bronchiëctasie?**

- Ja       Nee (ga verder naar vraag 15 op de volgende bladzijde)

